Major depressive disorder (MDD) is a major public health problem, adversely affecting cognition, with cognitive deficits affecting information processing speed, attention, memory, executive function, and working memory. In addition, cognitive deficits associated with MDD do not resolve after successful treatment of depressive symptoms. In one study, 94% of individuals with MDD and cognitive deficits at the start of treatment retained these deficits one year later, despite achieving clinical remission. Long-term maintenance of antidepressants does not prevent cognition decline, despite maintaining recovery from depression (Brunoni and Vanderhasselt, 2014; Ke et al., 2019; Mancuso et al., 2016). The present study aimed to evaluate the effectiveness of multi-session dorsolateral prefrontal cortex stimulation (in conjunction with cognitive stimulation) on working memory and academic performance in medical school students subjected to significant stressors and with a high prevalence of depression. Similar to single-session working memory enhancement studies, the anode will be placed over the dorsolateral prefrontal cortex and the cathode over the orbitofrontal prefrontal cortex (contralateral above the right eye).

HYPOTHESIS

CE + tDCS will be more effective compared to CE + tDCS-placebo or sham in improving scores on tests of working memory, cognitive functioning, P300 cognitive potentials, and academic performance in UNAM medical students with depressive symptoms at 15 treatment sessions (acute phase) and at 4 weeks of maintenance.

OBJECTIVES

To evaluate the effect of CE + tDCS to improve scores on working memory tests, cognitive functioning, P300 cognitive evoked potentials and academic performance in UNAM medical students with depressive symptoms vs simulated CE+ tDCS.

Specific objectives

1. To compare the presence of adverse effects and tolerability of both groups (EC+tDCS and EC+ tDCS- placebo or sham) at 15 treatment sessions (acute phase) and at 4 weeks of maintenance.
2. To describe the association of MEPs amplitude with performance on neurocognition and behavioral symptoms of both groups at 15 treatment sessions (acute phase) and at 4 weeks of maintenance.
3. To describe the association of P300 cognitive evoked potentials with performance in neurocognition and behavioral symptoms of both groups at 15 treatment sessions (acute phase) and at 4 weeks of maintenance.

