Cognitive stimulation application

Cognitive stimulation will require a printed manual and will be carried out in groups of 13 participants, three sessions per week for three weeks (acute) and one session per week for four weeks (maintenance). In the following table, the domains to be stimulated are specified, selected from the U.M.A.N. manual.

DOMAINS	SPECIFIC DOMAINS
Orientation	Space Temporary Staff
Memory	Episodic Visual

	Long-term visual Semantics Visual recognition Job
Attention	Sustained Divided
Language	Expressive (oral) Printed (written) Fluency
Praxias	Constructive
Gnosias	Visual Space
Reasoning	Sequencing
Calculation	Mental
Processing speed	Written Visual

Definition of clinical and neuropsychological improvement or response to treatment.

A positive intervention effect will be considered if there is a change or remains the same in the following dimensions of the previously described instruments and scales

- Cognitive:** remain the same or increase by 1 point on the Montreal Cognitive Assessment.
- Behavioral:** no decrease in Lawton & Brody Index and Katz Index values, and 1-point decrease in Cummings Neuropsychiatric Inventory (NPI).
- Neuropsychological:** increase one standard deviation in T-score of the values obtained for each scale.
- Electrophysiological:** increase MEP amplitude from the seventh stimulus onwards * $p>0.05$
- Global:** remain the same or have increased 1 point on the Clinical Global Impression Scale and 1 on the Everyday Life Memory Failure Questionnaire.

General procedure

Students will be recruited through the dissemination of the study at the School of Medicine.

In all cases, they must comply with the safety measures to be able to participate and will be evaluated in an initial interview to ensure that they meet the inclusion criteria. In this interview they will be explained in detail what the study consists of, and if they agree to participate and sign the informed consent letter, a time will be agreed upon for the baseline clinical evaluation. Each of the candidates who meet the selection criteria will be verbally invited to participate in the study after explaining the objectives and procedures of the study.

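### The response definition counts no change as a positive effect, is not tied to the sham comparison, and pairs p>0.05 with MEP while leaving out P300

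*Combined protocol and SAP*

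**What the plan says.** The section on clinical and neuropsychological improvement or response to treatment opens: "A positive intervention effect will be considered if there is a change or remains the same in the following dimensions of the previously described instruments". Five dimensions follow.

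- The Cognitive item is met by scores that "remain the same or increase by 1 point on the Montreal Cognitive Assessment".
- For the Behavioral item the rule asks for "no decrease in Lawton & Brody Index and Katz Index values", joined by 'and' to a fall of 1 point on the Neuropsychiatric Inventory (NPI).
- On the neuropsychological tests the requirement is to "increase one standard deviation in T-score of the values obtained for each scale".
- The one electrophysiological item reads "increase MEP amplitude from the seventh stimulus onwards * $p>0.05".
- Under the Global dimension, participants should "remain the same or have increased 1 point on the Clinical Global Impression Scale and 1 on the Everyday Life Memory Failure Questionnaire".

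The Hypothesis section sets a different standard: "CE + tDCS will be more effective compared to CE + tDCS-placebo or sham in improving scores on tests of working memory", and it goes on to name "P300 cognitive potentials, and academic performance in UNAM medical students with depressive symptoms". Statistical analysis sets p≤0.05 for all analyses. It plans a MANOVA with a group-by-time interaction on cognition, working memory and P300, with the stated purpose of testing therapeutic efficacy. It does not mention the response definition.

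**The concern.** A section headed improvement accepts stability, while the hypothesis is superiority over sham. Under General procedure both arms receive cognitive stimulation, which the Background credits with cognitive benefit. A sham participant can therefore meet the no-change items, or gain a point, with no tDCS effect at all. Because the definition is not linked to the group-by-time test, the protocol holds two standards for a positive result and does not say which governs. A report could follow the protocol's own wording and describe a positive effect without active stimulation having beaten sham.

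The electrophysiological item has two further faults. Its inequality contradicts the significance level, and it leaves out P300, the electrophysiological outcome that the hypothesis names and the plan describes in full.

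**Working it through.** The plan gives no figure for this definition, so there is none to reproduce. The check has two parts.

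**1. What an unchanged participant scores, item by item**

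| Dimension | Does no change qualify? |
|---|---|
| Lead sentence | Yes |
| Cognitive | Yes |
| Behavioral | Lawton/Katz part yes; whole bullet no, because the NPI must fall |
| Neuropsychological | No, a one-SD gain is required |
| Electrophysiological | No, an increase is required |
| Global | Yes if 'the same' also covers the memory-failure questionnaire; no if that scale must rise by 1 |

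No change therefore passes one dimension of five, or two, and the lead sentence conflicts with the other items in its own list.

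**2. Illustration of size**

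Inputs: 30 per arm, from the sample-size paragraph. Assumed, because the documents give no SD of change: change is a rounded normal variable with mean μ and SD 1 to 3 points, and 'increase by 1' means at least 1.

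Formulas: P(same or better) = Φ((μ+0.5)/SD); P(gain ≥1) = Φ((μ−0.5)/SD).

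With μ = 0:

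| SD | Same or better | Gain ≥1 | Qualifies only because 'same' counts |
|---|---|---|---|
| 1 | 0.691 (20.7 of 30) | 0.309 (9.3) | 0.383 (11.5) |
| 2 | 0.599 (18.0) | 0.401 (12.0) | 0.197 (5.9) |
| 3 | 0.566 (17.0) | 0.434 (13.0) | 0.132 (4.0) |

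These are single-scale rates and fit only the Montreal Cognitive Assessment item directly. For the compound bullets, additionally assume that their scales are independent:

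- Behavioral = P(same or better)² × P(gain ≥1), with an NPI fall of at least 1 treated as a gain. SD 1: 0.691² × 0.309 = 0.148. SD 3: 0.566² × 0.434 = 0.139. About 14–15%.
- Global, if the questionnaire must rise: 0.691 × 0.309 = 0.21 (SD 1) to 0.566 × 0.434 = 0.25 (SD 3).

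If cognitive stimulation alone gave 1 point in both arms (μ = 1, assumed), the single-scale rates become 0.933 to 0.691 for same or better and 0.691 to 0.566 for gain ≥1, for SD 1 to 3. Deleting 'the same' therefore does not isolate a tDCS effect; only a comparison with sham does.

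**3. The electrophysiological item set beside the rest of the plan**

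The item carries p>0.05; Statistical analysis uses p≤0.05 for all analyses. P300 is in the hypothesis, has full measurement definitions under Electrophysiological measurement, and is a MANOVA variable. MEP amplitude appears in specific objectives 2 and 4, but its procedure is only touched on: stimulator equipment (Figure 1 and Infrastructure), a 5 Hz paradigm (General procedure) and a TMS paradigm (Ethical considerations).

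**The case against.** The strongest reply is that the efficacy test lies elsewhere. Statistical analysis already compares the arms over time on cognition, working memory and P300, and no planned analysis uses the response definition. This stands. A reader might infer that the trial judges efficacy without reference to sham, or ignores P300. The documents do not support that; both gaps belong to this definition only.

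A reader might also infer that an unchanged participant is positive on most dimensions, or that 57–69% is the overall rate of false positives. Neither follows. Three of the five dimensions require movement, the Behavioral bullet is met by only about 14–15% under the same assumptions, and the plan does not say whether any or all dimensions must be met.

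The p>0.05 is probably a slip. It follows a stray asterisk, and the analysis section is clear about the level. It should not be read as an intention to count non-significance as success, but it still needs correcting. The definition can also be read at group level. On that reading a p-value is not out of place in kind, though its direction is still wrong and no comparison is named; on a participant-level reading it does not fit at all.

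Finally, the thin MEP references do not show that MEP is never recorded. They show only that its procedure and schedule are unclear.

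**Conclusion.** The definition is wrong as written and should be corrected. It accepts no change as a positive effect in its lead sentence and Cognitive item, and in Global on one reading. It names no comparison with sham and is not linked to the test that makes one. Its p-value contradicts the stated significance level, and its electrophysiological item uses MEP where the hypothesis and analysis use P300. These findings come from the text and need no assumptions.

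The consequence is limited to what may be called a response or a positive effect; the planned group-by-time efficacy test is untouched. The percentages illustrate one scale and rest on an assumed SD of change, a rounded normal model and no true change. The Behavioral and Global figures also assume independence between scales.

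**What to change.** 1. State in the definition that efficacy is judged only by the active-versus-sham group-by-time contrast in Statistical analysis. Make response a secondary descriptive measure, reported by arm and compared between arms.
2. Delete the wording that counts staying the same as a positive effect, or relabel those items as no worsening.
3. Remove the p-value from the response rule, or correct it to p≤0.05 as a group-level comparison between arms.
4. For electrophysiology, rely on the between-arm P300 comparison already planned. Do not add a participant-level P300 criterion without a threshold: under no true change, about half of participants would show a higher amplitude, and about half a shorter latency. Keep MEP and the named scales in the definition only if they are actually collected.

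The cost is wording, plus fewer participants counted as responders. A responder comparison with 30 per arm has low power. By Fisher's exact test (two-sided 0.05, assumed), a 20-point difference from a sham rate of 31–43% on a 1-point-gain item has about 26% power. For a true shift of 0.8 SD of change (assumed), that responder comparison has 57–59% power, against about 86% for a t test on change scores. Response should therefore stay secondary.

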4. To describe the association of risk factors with performance on neurocognition, behavioral symptoms and MEPs amplitude measure of both groups at 15 treatment sessions (acute phase) and at 4 weeks of maintenance.

RESEARCH STRATEGIES OR METHODS

Methods:

According to the classification of: Alvan Feinstein, this is a clinical trial, single-blind, comparative study (CE + active tDCS vs CE + sham tDCS), randomized, longitudinal and prospective.

The sample size was calculated with the G*Power 3.1 program with an effect size of 0.03 with a formula for factorial ANOVA (between-subjects, within-subjects and interaction effect) with 90%

power, at an alpha of 0.05, with 2 groups and 3 measurements, the final sample would be constituted by a total of 60 participants, which means 30 patients in each analysis group (Jacob Cohen, 1977). The sample will be divided into 2 experimental groups of undergraduates.

1. Group EC + tDCS active = 30
2. Group EC + simulated tDCS =30

Study population:

Selection criteria

Inclusion criteria

1. Age \geq 18 years old.
2. Vaccinated against SARS-COV2 virus.
3. Students of the Faculty of Medicine of UNAM
4. Fluent in Spanish.
5. Adequate visual and auditory acuity to be able to perform neuropsychological tests and cognitive stimulation.
6. Depressive symptoms with working memory impairment (diagnosed by applying a specific neuropsychological battery).
7. That they are not under antidepressant pharmacological treatment prior to entering the investigation.
8. Good general health without medical illnesses (systemic arterial hypertension, diabetes mellitus, dyslipidemias, infections, thyroid disease, vitamin deficiencies) that do not interfere with the study.
9. Willingness to participate in a scheduled 8-week study and able to attend scheduled evaluations.

Exclusion criteria

1. Any neurological disease that allows suspicion of cognitive failure other than depression, such as Parkinson's disease, multiple infarct dementia, Huntington's disease, hydrocephalus, brain tumor, progressive supranuclear palsy, seizure disorder, subdural hematoma, multiple sclerosis, history of head injury with loss of alertness.
2. Participants with a history of severe psychiatric disorders according to DSM-5 (bipolar disorder, schizophrenia, chronic depression) or psychotic features, agitation or behavioral problems in the last three months that could lead to difficulties in complying with the protocol.

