FAS (Controlled word association test) (Baseline and follow-up). Test that assesses verbal or phonetic fluency, as well as executive functions (cognitive flexibility, strategy, suppression of interference, inhibition of dominant responses), by evaluating the spontaneous pronunciation of words in one minute. The test consists of asking the patient to say as many words as possible, beginning with the letters provided by the evaluator. Normally the letters F, A, S are used, although others such as C, F, L can be used. A high educational level has been related to a better performance in the FAS test. Its use has been validated in numerous studies, showing a difference in the number of words pronounced in patients depending on their age, educational level and comorbidities (Kuslansky et al., 2004; Machado et al., 2009).

Hopkins Verbal Learning Test (Baseline and follow-up). Instrument that evaluates verbal memory. It was designed mainly for its application to older adults and population with neuropsychiatric disorders. It consists of 3 semantic fields, with 4 words each, which are read to the subject on three occasions so that he/she memorizes them. Subsequently, a recognition test is performed in which 12 target words, 12 distractor words, 6 words semantically related to the target words and 6 unrelated words are presented and the patient is asked to identify the previously memorized words. There are 6 equivalent forms of this test, so it is recommended for longitudinal studies, as the development of familiarity with the test is prevented. The Test-Retest correlation is similar to other tests that evaluate verbal memory such as the Wechsler Memory Scale. Its validity has been demonstrated in patients with head trauma, schizophrenia and dementia (Arango-Lasprilla et al., 2015) (Kuslansky, 2004).

Barcelona test (Baseline and follow-up). Neuropsychological test that quantitatively evaluates the patient's cognitive status. In its entirety the test assesses: orientation, language, reading, writing, visual recognition and abstract memory. There are three versions: a complete one with a duration of approximately 3 hours, an abbreviated one, with 45 minutes and aphasia profile.

Electrophysiological measurement

Cognitive evoked potentials:

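### Four of the five response domains rest on measures the protocol does not describe or schedule by name, no rule combines the domains, and several items count no change as success

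*Combined protocol and SAP*

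**What the plan says.** The section on the definition of improvement or response counts an intervention as positive if the participant changes or stays the same "in the following dimensions of the previously described instruments and scales". It then lists five domains:

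- Cognitive: "remain the same or increase by 1 point on the Montreal Cognitive Assessment".
- Behavioral: "no decrease in Lawton & Brody Index and Katz Index values", together with a 1-point fall on the Neuropsychiatric Inventory (NPI).
- Neuropsychological: "increase one standard deviation in T-score of the values obtained for each scale".
- Electrophysiological: a rise in MEP amplitude.
- Global: the same or 1 point higher on the Clinical Global Impression Scale, and 1 on an everyday memory-failure questionnaire.

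The section headed Instruments or tools describes four tests, each marked for baseline and follow-up: the complex figure, FAS verbal fluency, the Hopkins Verbal Learning Test and the Barcelona test. The last is introduced as a "Neuropsychological test that quantitatively evaluates the patient's cognitive status". The electrophysiology part that follows describes P300 latency, amplitude, reaction time and error rates. The General procedure refers to clinical and neuropsychological instruments without naming any. It places measurements at baseline, after the 15 sessions and at the end of maintenance.

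**The concern.** The documents supplied designate no single primary outcome, and this section is the only place that says what counts as success. If most of its measures are undefined, nobody can tell from the plan whether a given participant responded. Scales, versions and visits would then be settled later. The General procedure says that assessors also deliver the stimulation and know the allocation, so those choices could be made by people who are not blind.

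The gap also reaches the objectives. Specific objective 3 relates P300 to "performance in neurocognition and behavioral symptoms of both groups", and objectives 2 and 4 also use behavioural symptoms. The NPI is the only neuropsychiatric symptom scale named anywhere, and it appears only in the response definition.

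Finally, a criterion met by staying the same is a weak test of an add-on treatment when both arms receive cognitive stimulation.

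**Working it through.** The plan gives no figure to reproduce. The check matches each measure in the response definition against the sections on instruments, electrophysiology, procedure and analysis.

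**Match by domain**

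- Cognitive: 1 scale (Montreal Cognitive Assessment). Described elsewhere: 0.
- Behavioral: 3 scales (Lawton & Brody Index, Katz Index, NPI). Described elsewhere: 0.
- Neuropsychological: the described battery (complex figure, FAS, Hopkins, Barcelona). Described.
- Electrophysiological: MEP amplitude. No recording described. The nearest text is a picture of a magnetic stimulator, a 5 Hz paradigm mentioned alongside the P300 recording, and a reference to a TMS paradigm under Ethical considerations. The measure that is described in detail, P300, is not used in the definition.
- Global: 2 scales (Clinical Global Impression Scale, memory-failure questionnaire). Described elsewhere: 0.

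**Tally**

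- Scales named but not described: 1 + 3 + 2 = 6, of which 0 match the instruments section.
- Domains resting on those scales: 3 of 5.
- Adding the MEP domain: 3 + 1 = 4 of 5.
- Domains resting wholly on described tests: 5 − 4 = 1 of 5.

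**Could the scales be described elsewhere?** The two appendix references in the General procedure are to the stimulation-safety questionnaire and the adverse-effects questionnaire, not to outcome scales. The instruments section shows no redaction.

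**What the missing combining rule does.** Suppose only the Neuropsychological domain can be scored.

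- If all five domains are required, a participant who fails it is a non-responder, but one who passes cannot be classified.
- If any one domain suffices, a participant who passes is a responder, but one who fails cannot be classified.
- If three of five are required, nobody can be classified.

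None of these three rules classifies everyone from the described data.

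**Items that accept no change.** A participant with identical scores throughout would satisfy the Cognitive item, the daily-living part of the Behavioral item, and at least the Clinical Global Impression part of the Global item. Only the NPI part, the Neuropsychological item and the MEP item clearly require movement.

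**Use in the analysis.** The Statistical analysis section plans repeated-measures ANOVA and MANOVA on measures of cognition, working memory and P300. It does not mention the response definition.

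**The case against.** The strongest reply is that the defect is peripheral. The hypothesis and main objective concern scores on working memory, cognition, P300 and academic performance, not responder status, and the planned tests do not use the response definition. This stands, and it limits the consequence: the between-arm comparisons on described measures are unaffected.

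A second reply is that the instrument list may simply be incomplete. The General procedure speaks of clinical instruments, while all four listed tests are neuropsychological. Depressive symptoms are required for entry, yet no depression scale is described. This also stands. A reader might infer that the six scales are never administered, but the documents do not say so. They show only that the scales are neither described nor scheduled by name.

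A reader might also infer that the Behavioral domain cannot move in this population, because participants must be in good general health and exclusion 2 removes "psychotic features, agitation or behavioral problems in the last three months". The documents do not support that. Exclusion 2 goes on to limit itself to problems that could make it hard to comply with the protocol. Inclusion 6 requires depressive symptoms, so NPI scores need not start at zero, and a 1-point fall is impossible only for someone who does start there. Daily-living indices are plausibly near their maximum in healthy students, but no baseline scores are given, so this is an assumption. Even if it is right, it would make that half of the item uninformative, not impossible to score.

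**Conclusion.** The point holds in a limited form. Three of the five response domains depend on six scales that are neither described nor scheduled by name, and a fourth depends on MEP amplitude with no described recording. One domain of five can be scored in principle. No combining rule is given, and several items reward stability. The phrase pointing back to instruments already described is a false cross-reference, not an extraction gap.

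To say that response cannot be calculated at all would go too far. The Neuropsychological domain is usable, and whether an overall response can be derived depends on a combining rule that the plan does not state.

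The damage is to the stated definition of success and to the behavioural-symptom part of specific objectives 2 to 4. The view that the no-change items would separate the arms poorly is a judgement. It rests on both arms receiving cognitive stimulation and, for the daily-living indices, on the ceiling assumption. It is not a computed result.

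**What to change.** In the section defining response:

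1. Replace the Cognitive, Behavioral, Global and MEP items with criteria on measures already given at baseline, after the 15 sessions and at the end of maintenance: complex figure, FAS, Hopkins, Barcelona and P300. State which form of the Barcelona test is used, since three are listed. Since P300 is recorded under six stimulus sets (three auditory, three visual), state which ones count.
2. Require improvement, with a stated direction and threshold for each measure. Do not accept no change.
3. State how the domains combine into an overall response and at which assessment.
4. Report response by arm.

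If a behavioural measure is kept for specific objectives 2 to 4, name it and schedule it at all three assessments. The protocol names no depression score that could simply be reused. Objectives 2 and 4 also use MEP amplitude, so either describe its recording or revise those objectives.

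These changes should be made before outcome data are seen. Redefining response on the existing battery costs only wording and adds no visit or participant. A named behavioural measure would add a short assessment at each of the three time points. The small loss is a global rating that was never scheduled by name.

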-King's Figure (Basal and tracking). This instrument aims to investigate perceptual organization and visual memory in brain-injured individuals. It evaluates memory and perception. Time of Application: The time taken is the time that the copy lasts. It is taken in two stages: copying phase and memory reproduction phase. It uses the following materials: paper, white sheets, colors, pencils. Its application is individual and the time is variable, around 10 minutes. It evaluates perceptual organization and visual memory in individuals with brain injury, by reproducing the memory figure after a period of interference. It assesses the ability to organize and plan strategies for problem solving, as well as their visoconstructive ability. Its application consists of asking the subject examined to copy a complex figure by hand and without time limit and subsequently, without prior warning and without the help of the model, the examinee must reproduce immediately and after 30 minutes again the same figure, in order to assess his capacity for non-verbal material recall. Each unit can earn the subject up to two points. 2 points are given when the drawing is correct in shape and location. 1 point is given when the location or shape of the unit is missed. 0 points are given when it fails to place the location or shape of the unit. Each application is scored on a scale ranging from 0 to 36 points. Score $1/2$ of an adult =32 points. The memory session is scored in the same manner as the scoring units in the particular areas or details of the figure have been numbered for ease of scoring. A comparison of the scores corresponding to each session will help the clinician determine the presence of visuo-graphic or visuo-memory deficits, as well as their relative severity (Rey, 1996; Rivera et al., 2015).

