Prior to entry into this research project, the participant will have read and discussed the informed consent document with the principal investigator. Those who agree to participate will be asked to review and sign the informed consent form once all questions have been answered. All participants will be assigned a registration number. They will be given a booklet with information on cognitive stimulation and another on neuromodulatory techniques (rTMS and tDCS).

Subsequently, a clinical interview will be conducted to capture relevant demographic and clinical data, and the clinical and neuropsychological instruments will be applied for diagnostic certainty, which

in turn will count as baseline measurement. The total application of the instruments could be done in one session (3 hours with a 15-minute break). After that, the questionnaire of stimulation safety measures will be applied (see APPENDIX) and the recording of P300 potentials will be carried out with the application of the 5 Hz paradigm. The following measurements will be taken at the end of the 15 sessions and at the end of maintenance.

The patient will then be randomly assigned to one of the two tDCS groups and will be given 15 sessions, 5 per week from Monday to Friday and then one per week for 4 weeks. After each session, adverse effects will be asked about and recorded in a questionnaire (see APPENDIX). They will be evaluated at the beginning, at the end of the 15 sessions (three weeks) and four weeks after the end of the study maneuver (the characteristics of each maneuver are described in the methods section corresponding to each stimulation technique). At the same time, all participants will receive three sessions per week of cognitive stimulation using the manual adapted to Mexican Spanish of the UMAM method.

The randomization will be carried out with a list of numbers in Excel that will be in charge of one of the members of the research who will not have contact with the participants.

The applicators of the stimulation techniques will be the same as the assessors and will not remain blind to the maneuver, unlike the students. All applicators will be randomized to form the two groups and the applicator of the techniques will know whether it is the experimental maneuver or the placebo maneuver.

Statistical analysis

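### The neuropsychological response rule credits a within-person one-SD gain to the intervention with no comparison with sham, so some sham students will meet it without any tDCS effect

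*Combined protocol and SAP*

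**What the plan says.** The section defining clinical and neuropsychological improvement opens: "A positive intervention effect will be considered if there is a change or remains the same in the following dimensions". Its neuropsychological line then requires the student to "increase one standard deviation in T-score of the values obtained for each scale". It does not mention the sham arm. It also does not say whether all scales must meet the mark or each is judged alone, which SD is meant (norm or sample), or at which follow-up visit.

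The Instruments section describes four neuropsychological tests: the complex figure ("Each application is scored on a scale ranging from 0 to 36 points"), the "FAS (Controlled word association test) (Baseline and follow-up"), the "Hopkins Verbal Learning Test (Baseline and follow-up") and the Barcelona test.

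Inclusion criterion 6 is "Depressive symptoms with working memory impairment (diagnosed by applying a specific neuropsychological battery"). It gives no cut-off and does not name the tests that decide entry. Under General procedure, "the clinical and neuropsychological instruments will be applied for diagnostic certainty, which" "in turn will count as baseline measurement". The same section gives cognitive stimulation to every participant in both arms.

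The Statistical analysis section plans repeated measures ANOVA and MANOVA on the scores, with time and interaction effects. Baseline variables enter as covariates only if the arms differ at p<0.05. It describes no analysis of responders.

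**The concern.** A rule that compares a student only with his or her own earlier score cannot separate tDCS from anything else that moves the score. Four such influences are built into this design: ordinary retest error, practice on repeated tests, the cognitive stimulation given to both arms, and regression to the mean on any scale whose low score brought the student into the trial. A sham student can therefore be recorded as showing a positive intervention effect.

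The wording also gives very different response rates depending on how *each scale* is read, and it conflicts with a lead-in under which an unchanged score is already positive. Since no analysis of response is specified, the reading could be chosen after the data are seen. The same influences raise the within-arm time effect, which the plan intends to examine.

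**Working it through.** The plan states no response rate, retest correlation or impairment cut-off, so there is no figure of its own to reproduce. The sizes below rest on assumptions.

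**Inputs.** From the plan: a gain of 1 SD, four scales, 30 students per arm. Assumed: scores in SD units with equal variance at both visits and normal errors; retest correlation r from 0.6 to 0.9; where selection applies, entry at or below -1 SD; correlation between gains on different scales from 0 to 0.7.

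**Step 1. One scale, no true change, no selection.** The change has SD √(2(1−r)), so P(gain ≥ 1) = 1 − Φ(1/√(2(1−r))).

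| r | SD of change | 1/SD | P(gain ≥ 1 SD) |
|---|---|---|---|
| 0.6 | 0.894 | 1.118 | 13.2% |
| 0.7 | 0.775 | 1.291 | 9.8% |
| 0.8 | 0.632 | 1.581 | 5.7% |
| 0.9 | 0.447 | 2.236 | 1.3% |

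Per arm of 30 this is about 0.4 (30 × 0.013) to 4.0 (30 × 0.132) students.

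**Step 2. One scale used for entry at −1 SD or below, no true change.** The mean entry score is −φ(1)/Φ(−1) = −1.525. The expected rise is (1−r) × 1.525. Given entry score x, the retest score is normal with mean rx and variance 1−r². Averaging P(retest − x ≥ 1) over x ≤ −1 gives the last column.

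| r | Expected rise (SD) | P(gain ≥ 1 SD) |
|---|---|---|
| 0.6 | 0.61 | 32% |
| 0.7 | 0.46 | 23% |
| 0.8 | 0.31 | 13% |
| 0.9 | 0.15 | 2.7% |

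Per arm of 30: about 0.8 (30 × 0.027) to 9.6 (30 × 0.32) students.

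**Step 3. Practice or training gain shared by both arms.** With an illustrative mean gain of 0.3 SD and no selection, P = 1 − Φ(0.7/√(2(1−r))). This gives 22%, 18%, 13% and 6% at r = 0.6, 0.7, 0.8 and 0.9.

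**Step 4. All four scales must meet the mark, true gain 0.5 SD on each, no selection.** Per scale, p = 1 − Φ(0.5/√(2(1−r))), which is 0.288 at r = 0.6 and 0.132 at r = 0.9.
- Independent gains: p⁴ = 0.288⁴ = 0.7% at r = 0.6, and 0.132⁴ = 0.03% at r = 0.9.
- Gains correlated 0.7 (multivariate normal): 11% at r = 0.6, and 3.3% at r = 0.9.

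The top of this range is about 3 of 30 students (30 × 0.11).

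**The case against.** The strongest reply is that the rule is not the planned test. The Statistical analysis section compares continuous scores between groups over time. Retest error, practice, training and regression to the mean act alike in randomised arms, so the interaction test is not invalidated. That stands, and it limits this point to how response and within-arm change are described.

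The sizes are also fragile, and this stands too. No reliability or cut-off is given in the plan. At r = 0.9, chance response on one scale is only 1.3%, or 2.7% with selection. The selection figures apply only to a scale that decides entry. Entry is on working memory, and the Instruments section does not describe any of its four tests as a working memory test. The procedure also checks inclusion at an initial interview before scheduling the baseline evaluation, so how far the scores that decide entry are also the baseline scores is not fully settled.

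A reader might infer several stronger things that the documents do not support:
- *That almost nobody can respond.* This needs the all-scales reading with weakly correlated gains. Regression to the mean makes response easier, not harder.
- *That a large share respond by chance on at least one of the four scales.* Meeting the mark on any one scale is not a reading the text offers.
- *That untreated students respond.* No student is untreated.
- *That the rule cannot reflect tDCS at all, or that a real benefit would be missed.* An active-minus-sham difference in response would still reflect tDCS, with noise (setting aside that assessors know the allocation), and the planned tests do not use the rule.

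**Conclusion.** The point holds in limited form. The plan labels a within-person gain an intervention effect, with no sham comparison, in a design where several other causes produce that gain. It also contradicts its own lead-in and leaves the combination of scales open. With no true change, expect about 1% to 13% to meet the mark on an unselected scale, and about 3% to 32% on a scale used for entry, with an expected rise of 0.15 to 0.61 SD. Under the all-scales reading with a true 0.5 SD gain, expect from under 1% up to about 11%. These ranges depend on the assumed retest correlation, entry cut and correlation between gains. The textual defects do not depend on them. What is affected is the meaning of response and any reading of the within-arm time effect, not the validity of the between-group tests.

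**What to change.** 1. Reconcile the rule with its lead-in and apply it scale by scale, stating which SD and which visit are meant.
2. Keep it only as a secondary description, reported as the active-minus-sham difference in proportions with a 95% CI.
3. Base the neuropsychological conclusion on the between-arm difference in each scale's follow-up T-score, adjusted for that scale's baseline whether or not the arms differ at baseline at p<0.05.
4. State that within-arm change will not be read as benefit.

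The scales should not be replaced by one equal-weight average. Averaging fluency, figure, verbal memory and general status could hide or dilute a gain on a single scale.

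The cost is small: the same data and visits, a little more analysis, and response rates that look less favourable because sham response is set against them.
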